6.4 Monitoring for hepatitis C virus reactivation

At screening, HCV-RNA will be tested using quantitative RNA-PCR in patients with HCV Ab positivity and in patients with known or suspected past hepatitis C virus infection (including patients with past interferon 'curative' treatment).

Patients with detectable HCV RNA at baseline will be excluded. Patients known to have a history of HCV infection, despite a negative viral load test at screening (including those that were treated and are considered 'cured') will be monitored for HCV reactivation on Day 1 of every cycle, at end of lenalidomide (within 1 week after stopping study drug), and at 28-day follow-up visit (\pm 7 days of scheduled visit).

In patients with known past hepatitis C infection with undetectable HCVRNA levels at baseline, reactivation will be defined by the new appearance of detectable HCV-RNA; in this case, lenalidomide must be discontinued.

6.5 Flow chart

6.5.1 Screening

All eligible patients will receive the following assessments:

- Medical history
- Clinical and laboratory evaluation
- Imaging documentation of therapy response (CT, MR, other)
-

6.5.2 Initial examinations

- Informed consent
- Medical history
- Concomitant medications
- Vital signs (pulse, blood pressure, weight and height)
- Physical examination including ECOG Performance Status
- CBC
- Biochemistry: creatinine, uricemia, AST, ALT, GGT, ALP, total and direct bilirubin, LDH, beta2-microglobulin, Nat, Kal, Ca
- HIV, HCV, HBV testing
- Pregnancy test (for FCBP only)

6.5.3 Interim examinations (every week for the first 8 weeks, then every 2 weeks)

- Concomitant medications
- Vital signs (pulse, blood pressure, weight and height)
- Physical examination including ECOG Performance Status
- CBC

OSPEDALE SAN RAFFAELE
ISTITUTO DI RICOVERO E CURA A CARATTERE SCIENTIFICO

- Biochemistry
- Disease status evaluation (contrasted total body CT scan every 4 months)
- AE reports

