2.3 Primary endpoint

- One-year progression free survival (PFS)

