5.1 Treatment

After the documentation of PR or CR after salvage chemo-immunotherapy, patients will receive lenalidomide 25 mg daily orally for 21 days every 28 days for 2 years (24 cycles). This maintenance therapy will start after one month from salvage chemotherapy conclusion. The duration of period between the end of chemotherapy and the beginning of maintenance treatment can be variable according to the achievement of the acceptable haematological and biochemical parameters. This interval could be prolonged until the patient will be considered eligible for the trial, within 2 months.

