6.5.4 Post-study surveillance evaluation (until 1 year after lenalidomide discontinuation)

- Concomitant medications
- Vital signs (pulse, blood pressure, weight and height)
- Physical examination including ECOG Performance Status
- CBC
- Biochemistry
- Disease status evaluation
- AE reports

6.5.5 Follow-up (every 4 months for the 2nd to the 4th year; every 6 months for the 5th and 6th, yearly afterward)

- Physical examination including ECOG Performance Status
- CBC
- Biochemistry
- Disease status evaluation (contrasted total body CT scan plus every procedure positive at first relapse (marrow biopsy according to clinical requirements)

7 Data quality assurance

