8.1 Sample size and power consideration

Simon's two-stage optimal design will be used. The null hypothesis that the true 1-year PFS is 30% will be tested against a one-sided alternative. In the first stage, 15 patients will be accrued. If there are 5 or fewer patients progression-free at one year in these 15 patients, the study will be stopped. Otherwise, 32 additional patients will be accrued for a total of 47. The null hypothesis will be rejected if 19 or more patients progression-free at one year are observed in 47 patients. This design yields a type I error rate of 5% and power of 80% when the true 1-year PFS is 50%.

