8.2.2 Progression-free survival

It is defined as the time from enrolment to progression or relapse of lymphoma (if post-induction disease status was PR or CR, respectively). Patients alive at last follow-up will be censored.

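### One-year PFS is decided by a 4-monthly CT with no stated anchor, window or 12-month classification rule, so progressions first documented after day 365 can count as successes

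*Combined protocol and SAP*

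**What the plan says.** - **Endpoint and origin.** Section 2.3 names "One-year progression free survival (PFS") as the primary endpoint. Section 8.2.2 sets the clock: "It is defined as the time from enrolment to progression or relapse of lymphoma".
- **Decision rule.** Under section 8.1, the trial stops if 5 or fewer of the first 15 patients are progression-free at one year. It succeeds if "19 or more patients progression-free at one year are observed in 47 patients".
- **Imaging.** Section 6.5.3 lists "Disease status evaluation (contrasted total body CT scan every 4 months") among visits headed "6.5.3 Interim examinations (every week for the first 8 weeks, then every 2 weeks"). The same visits include physical examination, performance status, blood count and biochemistry.
- **After stopping the drug.** The heading "Post-study surveillance evaluation (until 1 year after lenalidomide discontinuation") in section 6.5.4 covers the following year. Its list includes disease status evaluation, without a modality or an interval. Sections 6.5.3 and 6.5.5 give both.
- **Population.** Section 8.4 analyses all enrolled subjects. Section 4.3.1 treats stopping for toxicity as a regular end of study participation.
- **Not in the supplied text.** The date from which the 4-monthly scans run, a scan window, the lag from enrolment to first dose, a rule for dating progression, and a rule for classifying a patient whose deciding scan falls after day 365 or is missing.

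**The concern.** A binary count at a fixed date needs an assessment tied to that date. Here the third 4-monthly scan lands nominally on the one-year mark and nothing says which side it should fall. Read literally, a patient whose progression is first documented on day 370 was progression-free at one year and adds one to the success count. The same holds for a patient who stopped treatment in year 1, progressed before day 365 and was not imaged until later.

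Both routes work in one direction: late detection can turn a failure into a success, never the reverse. They affect the decision at 15 patients as well as the one at 47. In a single-arm trial, no concurrent group shares the same detection delay and offsets it. The stake is the false-positive rate of the primary test.

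**Working it through.** **1. The plan's own design.** With 15 patients in stage 1 (continue if 6 or more) and 32 more in stage 2 (reject if 19 or more of 47):

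P(success | p) = Σ over x = 6 to 15 of P[Bin(15, p) = x] × P[Bin(32, p) ≥ 19 − x]

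- p = 0.30 gives 0.0588.
- p = 0.50 gives 0.815.

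The stated 80% power is met. The stated 5% type I error is not quite met by the printed rule, which is a separate matter. The reference value below is 5.9%.

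**2. Where the third scan falls.** Day of scan 3 = 12 × month length + lag, where lag is the unstated time from enrolment to whatever date starts the scan calendar.

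| Month convention | Day of scan 3 | After day 365 if |
|---|---|---|
| Calendar | about 365 + lag | any lag, or a late visit |
| 30 days | 360 + lag | lag over 5 days |
| 28 days | 336 + lag | lag over 29 days |

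The 28-day line is plausible because section 5.1 equates 24 cycles of 28 days with 2 years. The text does not choose among these.

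**3. Effect of late documentation.** Assumptions: exponential PFS, a true one-year rate of 30% taken as free of detection delay, calendar months and no lag.

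- Month-8 PFS = 0.30^(8/12) = 0.448.
- Progressing between months 8 and 12: 0.448 − 0.300 = 0.148 of patients.
- If a fraction f of these is first documented after day 365, apparent rate = 0.30 + f × 0.148.

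| f | Apparent rate | P(pass stage 1) | P(success) |
|---|---|---|---|
| 0 | 30.0% | 28% | 5.9% |
| 10% | 31.5% | 32% | 8.8% |
| 25% | 33.7% | 39% | 14.9% |
| 50% | 37.4% | 51% | 29.1% |
| 100% | 44.8% | 73% | 63.4% |

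With a 30-day lag, scan 2 also moves later and catches more. The success probabilities for f = 10%, 50% and 100% become 7.9%, 20.4% and 44.0%.

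**4. Early stoppers, taken separately.** Suppose 10% of enrolled patients stop while progression-free at month 4 and none of their progressions is detected by month 12.

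- Month-4 PFS = 0.30^(4/12) = 0.669.
- P(progress in months 4–12, given progression-free at 4) = 1 − 0.30/0.669 = 0.552.
- Apparent rate = 0.30 + 0.10 × 0.552 = 0.355; P(success) = 21%.
- If half of those progressions are detected in time: 0.30 + 0.05 × 0.552 = 0.328; P(success) = 12%.

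The 10% stopping rate is illustrative; the documents give none.

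**The case against.** A reader might infer that the scans run on the treatment calendar, that the third one will fall after day 365, and that the real landmark is therefore month 8. The documents do not support that chain.

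- **Anchor.** Placing CT under the interim examinations suggests on-treatment timing, but no anchor is stated. Counting from enrolment is not excluded.
- **Lag.** Section 5.1 says "This maintenance therapy will start after one month from salvage chemotherapy conclusion" and adds "This interval could be prolonged until the patient will be considered eligible for the trial, within 2 months". That gap runs from the end of chemotherapy and may lie wholly before enrolment.
- **Month length.** On 28-day months with no lag, scan 3 falls at day 336. Even if every later progression waits for scan 4, the apparent rate is 0.30^(336/365) = 33.0% and the rule succeeds 12.8% of the time, far below 63%.
- **Clinical detection.** Visits every one to two weeks, in what section 1.3 calls aggressive lymphoma, will reveal some progressions before a scan does. The 63% figure requires that none be found this way.
- **Early stoppers.** Section 6.5.4 does list disease status evaluation, so it would be wrong to say these patients go unassessed. Section 6.1.2 also schedules survival-status contacts every four months after treatment, although it does not specify imaging at them.
- **Benchmark.** The source of the 30% null is not given. If it came from data with similar scan spacing, it already contains some detection delay and the net inflation is smaller.
- **Appendix E.** The response criteria are listed but are not in the supplied text, so a dating rule there cannot be excluded.

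These points stand, and they make the size conditional. They do not supply an anchor, a window or a classification rule. The 28-day case shows that a scan before the cut-off also leaves a stretch unobserved unless a window and rule are set.

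**Conclusion.** The point holds as a gap in how the primary count is made. On the supplied text, one-year status cannot be classified unambiguously. Following the plan literally can record a patient who progressed within the year as a success, and for early stoppers the timing and modality of the deciding assessment are left open.

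The direction is certain and the magnitude is not. On the step 3 assumptions, the false-positive probability is about 9%, 15% or 29% when 10%, 25% or 50% of month 8–12 progressions are documented late, against 5.9% when none is. The 63% is a ceiling that needs every third scan late and no clinical detection. The 21% for early stoppers is likewise an upper scenario. Neither is a prediction of what the trial will show, and a 30% benchmark built on similar scan timing would reduce all of these figures.

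**What to change.** Amend sections 6.5.3, 6.5.4 and 8.2.2 together:

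1. Time disease assessments from enrolment, at months 4, 8 and 12, whether or not lenalidomide continues.
2. Define one-year status by the month-12 CT within a prespecified window.
3. Count progression found on that CT as failure at one year, even when the scan date is after day 365.
4. State how patients without an evaluable month-12 status are counted, for example as not progression-free in the primary count, with a Kaplan–Meier one-year estimate as a sensitivity analysis.

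Items 3 and 4 are conventions, and others could be defended; what matters is fixing them in advance. The cost is protocol wording, a few scans re-timed or retained for patients who stop early, and a slightly less favourable one-year rate.

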6.5.4 Post-study surveillance evaluation (until 1 year after lenalidomide discontinuation)

- Concomitant medications
- Vital signs (pulse, blood pressure, weight and height)
- Physical examination including ECOG Performance Status
- CBC
- Biochemistry
- Disease status evaluation
- AE reports

6.5.5 Follow-up (every 4 months for the 2nd to the 4th year; every 6 months for the 5th and 6th, yearly afterward)

- Physical examination including ECOG Performance Status
- CBC
- Biochemistry
- Disease status evaluation (contrasted total body CT scan plus every procedure positive at first relapse (marrow biopsy according to clinical requirements)

7 Data quality assurance

7.1 Quality control

The investigators will assure the monitoring of the clinical study to assure conformance to protocol as well as the completeness, correctness and plausibility of the completed case report forms (CRF).

7.2 Deviation from study protocol

Every deviation from the trial protocol must be specified and documented separately for each patient. The investigator is responsible of discussing the type and extent of deviation as well as the possible consequences for further participation of the patient in the study.

8 Statistical procedures

8.1 Sample size and power consideration

Simon's two-stage optimal design will be used. The null hypothesis that the true 1-year PFS is 30% will be tested against a one-sided alternative. In the first stage, 15 patients will be accrued. If there are 5 or fewer patients progression-free at one year in these 15 patients, the study will be stopped. Otherwise, 32 additional patients will be accrued for a total of 47. The null hypothesis will be rejected if 19 or more patients progression-free at one year are observed in 47 patients. This design yields a type I error rate of 5% and power of 80% when the true 1-year PFS is 50%.

8.2 Efficacy endpoints

8.2.1 Overall survival

It is defined as the time from enrolment to death for any cause. Patients alive at last follow-up will be censored.

8.2.2 Progression-free survival

It is defined as the time from enrolment to progression or relapse of lymphoma (if post-induction disease status was PR or CR, respectively). Patients alive at last follow-up will be censored.

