Design:	Simon's two-stage optimal design will be used. The null hypothesis that the true 1-year PFS is 30% will be tested against a one-sided alternative. In the first stage, 15 patients will be accrued. If there are 5 or fewer patients progression-free at one year in these 15 patients, the study will be stopped. Otherwise, 32 additional patients will be accrued for a total of 47. The null hypothesis will be rejected if 19 or more patients progression-free at one year are observed in 47 patients. This design yields a type I error rate of 5% and power of 80% when the true 1-year PFS is 50%.
Number of patients:	47
Timelines:	Anticipated start: July 2009 Recruitment period: July 2009 – December 2015 Final report: December 2016

San Raffaele Scientific Institute
Division of OncoHematological Medicine
Department of OncoHematology
[name]
20132 - Milano

OSPEDALE SAN RAFFAELE
ISTITUTO DI RICOVERO E CURA A CARATTERE SCIENTIFICO

LIST OF ABBREVIATIONS / DEFINITION OF TERMS

ADR	Adverse Drug Reaction
AE	Adverse Event
ALT (SGPT)	Alanine transaminase (serum glutamate pyruvic transaminase)
ANC	Absolute neutrophil count
ASCT	Autologous stem cell transplantation
AST (SGOT)	Aspartate transaminase (serum glutamic oxaloacetic transaminase)
β-hCG	Beta-human chorionic gonadotropin hormone
β2M	Beta-2 Microglobulin
BUN	Blood urea nitrogen
CBC	Complete blood count
CR	Complete remission
CRF	Case report form
CT	Computed tomography
CTC	Common toxicity criteria
DLT	Dose-limiting toxicity
EC	Ethics Committee
ECG	Electrocardiogram
ECOG	Eastern Cooperative Oncology Group
EMEA	European Agency for Evaluation of Medicinal Products
FCBP	Female of child bearing potential
FDA	Food and Drug Administration
GCP	Good Clinical Practice
CC-5013	(lenalidomide)
ICH	International Conference on Harmonization
IDMC	Independent Data Monitoring Committee
IMiD	Immunomodulatory drug
IRB	Institutional Review Board
LDH	Lactate dehydrogenase
LLN	Lower Limit of Normal
MedDRA	Medical Dictionary for Regulatory Activities
MITT	Modified Intent-to-Treat
MR	Magnetic Resonance
NCI	National Cancer Institute
OS	Overall survival
PD	Progressive disease
PFS	Progression free survival
PR	Partial remission
SAE	Serious adverse event
SD	Stable disease

*San Raffaele Scientific Institute
Division of OncoHematological Medicine
Department of OncoHematology
[name]
20132 - Milano*

OSPEDALE SAN RAFFAELE
ISTITUTO DI RICOVERO E CURA A CARATTERE SCIENTIFICO

SOP
TSH
TTF
TPP
ULN
WBC

Standard Operating Procedure

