6.1.2 Survival status

Patient survival status will be determined every four weeks during the study treatment, every four months for three years after, every six months for the following two years and every year after there, until 10-year follow-up completion, progression or death.

In addition to reporting the serious adverse events, patient's deaths must be recorded continuously throughout the study.

Evaluation and documentation of the cause of death must be entered in the CRF.

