8.4 Efficacy analysis

Efficacy analyses will be performed on the intention-to-treat population that includes all subjects enrolled. Response rate during and after lenalidomide treatment will be provided. Analyses will be performed to characterize PFS, TTP and OS. The Kaplan-Meier procedure will be used to characterize the time-to-event curves in the analyses where there is censoring. Otherwise, summary statistics (mean, standard deviation, median, minimum and maximum) will be provided. Parameters known to be potentially predictive of disease aggressiveness and

OSPEDALE SAN RAFFAELE
ISTITUTO DI RICOVERO E CURA A CARATTERE SCIENTIFICO

likelihood of response to lenalidomide in relapsed or refractory DLBCLs (tumour burden, LDH levels, time from last rituximab, etc) as well as prognostic subtypes (namely “germinal-center B cell type” – GBC - and “activated B-cell type” – ABC) or specific gene expression patterns/genetic signatures amenable to DLBCL subtypes - where available - will be taken into consideration in post-hoc multivariate efficacy analysis.

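### The primary endpoint, one-year PFS, does not say how a death without progression is counted, and the two-stage decision count does not require patients to be alive

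*Combined protocol and SAP*

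**What the plan says.** Section 2.3 names one-year PFS as the primary endpoint. Section 8.2.2 defines it: "It is defined as the time from enrolment to progression or relapse of lymphoma (if post-induction disease status was PR or CR, respectively"). The only other rule there is "Patients alive at last follow-up will be censored". Section 8.2.1, directly above, does name death for overall survival: "It is defined as the time from enrolment to death for any cause".

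The decision rule in section 8.1, repeated in the synopsis, works on counts of patients. At stage 1, "If there are 5 or fewer patients progression-free at one year in these 15 patients, the study will be stopped". At the end, "The null hypothesis will be rejected if 19 or more patients progression-free at one year are observed in 47 patients". Neither sentence mentions being alive.

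Section 8.4 analyses everyone enrolled and treats TTP as separate from PFS: "Analyses will be performed to characterize PFS, TTP and OS". Section 8.2 has no definition of TTP. Section 6.1.2 requires that "deaths must be recorded continuously throughout the study" and that "Evaluation and documentation of the cause of death must be entered in the CRF", so the facts needed to classify a death will be on file.

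**The concern.** Consider a patient who dies in remission at month five. Under 8.2.2 there is no event, because the lymphoma has not progressed. There is no censoring either, because the patient is not alive at last follow-up. Under 8.4 the patient stays in the denominator. Under 8.1 it is unclear whether the patient counts as progression-free at one year. Read literally, the text can leave such a death out of the failures at both decision points.

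These deaths are foreseeable. Section 4.1 admits ECOG scores up to 3, the rationale in section 1.3 describes patients over 65 or unfit for transplant, treatment runs for up to 24 cycles, and section 6.2.1.1 provides a category for deaths attributed to the study drug. A death in remission on maintenance therapy should not be scored as a success.

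The stage-1 stop and the final claim of activity both rest on this endpoint. When a count is one short of a cut-off, the classification of a single such death decides the outcome. In an open-label, single-arm trial, an unwritten rule would be settled by people who know the outcomes.

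**Working it through.** **Inputs (section 8.1).** Stage 1 has 15 patients and continues with 6 or more successes. The total is 47 (15 + 32), with rejection at 19 or more. The null is 30% and the alternative 50%. The documents give no rate of death without progression, so that rate is varied below as an assumption.

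**Formula.** With p the probability that a patient is counted as a success:

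P(reject) = Σ over x = 6,…,15 of Bin(x; 15, p) × P(Bin(32, p) ≥ 19 − x).

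**The plan's own figures.** At p = 0.30, P(continue) = 0.278 and P(reject) = 0.0588. At p = 0.50, P(continue) = 0.849 and P(reject) = 0.815. The stated power of 80% is met. The type I error is 5.9%, not the stated 5%. That mismatch is a separate matter, unrelated to deaths (the same cut-offs with 46 patients give 0.0499). Here 5.9% is simply the baseline.

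**Reading 1: deaths are failures.** p stays at 0.30 and P(reject) stays at 0.0588. There is no inflation.

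**Reading 2: deaths are counted as progression-free, and the 30% null refers to a progression-only endpoint.** The null and the count then match, so p is again 0.30 and P(reject) is 0.0588.

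**Reading 3 (worst case): deaths are counted as progression-free, and the true death-inclusive PFS is 30%.** Let s be the share of first-year failures that are deaths without progression. Then p = 0.30 + 0.70s, and the expected number of such deaths is 47 × 0.70 × s.

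| s (assumed) | Deaths in 47 | p | P(continue) | P(reject) |
|---|---|---|---|---|
| 5% | 1.6 | 0.335 | 0.387 | 0.142 |
| 10% | 3.3 | 0.370 | 0.501 | 0.273 |
| 15% | 4.9 | 0.405 | 0.612 | 0.435 |
| 20% | 6.6 | 0.440 | 0.713 | 0.599 |

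Solving for p instead, P(reject) reaches 0.10 at p = 0.3198, which is 47 × 0.0198 = 0.93 deaths. It reaches 0.20 at p = 0.3519, which is 47 × 0.0519 = 2.44 deaths.

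**Reading 4: deaths are censored in the Kaplan-Meier analysis.** With constant hazards and death-inclusive one-year survival of 0.30, the curve estimates 0.30^(1 − s): 0.319, 0.338, 0.359 and 0.382 for s = 5, 10, 15 and 20%. The cut-offs apply to counts and not to this estimate, so the result is an upward bias in the reported rate and not a decision error.

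**Room for one death to decide.**
- At p = 0.30, P(exactly 5 of 15) = 0.206, and P(continue, then exactly 18 of 47) = 0.032. At p = 0.50 these are 0.092 and 0.018.
- These are upper bounds, because at least one failure must also be a death without progression. For stage 1 at p = 0.30 there are ten failures, so the joint probability is 0.206 × [1 − (1 − s)^10]. This is 0.206 × 0.401 = 0.083 at s = 5% and 0.206 × 0.893 = 0.184 at s = 20%.

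**The case against.** The best case for the plan is that the intent is clear enough. The endpoint is called progression-free survival. Only living patients are censored, TTP is listed apart from PFS, and a patient who has died cannot be observed progression-free at one year. Section 6.1.2 ends follow-up at progression or death, and section 4.3.1 lists death beside lymphoma failure as a regular end of participation. On that reading the decision rule is sound and the repair is a few words. The large rejection probabilities need the least plausible reading, an assumed death share, and a 30% null that includes death.

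Much of this stands. The intent is probably that deaths are failures. The 14% to 60% range is an illustration only; its top end implies 6.6 such deaths among 47 patients who entered in response and were screened for serious illness. If the null is progression-only, there is no inflation at all.

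It does not close the gap. The censoring sentence is word for word the one used for overall survival and, taken literally, would also censor living patients who have progressed, so it is weak evidence of a considered PFS rule. TTP is undefined, and the event in 8.2.2 is the one a TTP definition would normally use. Sections 4.3.1 and 6.1.2 govern participation and follow-up, not the endpoint. Appendix E was not available for this check; section 6.1.1 cites it for response, and 8.2.2 does not refer to it.

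**Conclusion.** The concern holds. As written, the primary endpoint leaves a death without progression with no status, and nothing in the available text makes it a failure. This is certain from the wording and rests on no assumption.

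The size of the effect is conditional. It is zero if deaths are failures, or if the 30% null excludes death in the same way as the count. If the null includes death but the count does not, about one such death in 47 on average is enough to take the chance of a false positive from 5.9% to 10%. Because the choice can change both decisions and would otherwise be made with outcomes known, the definition must be corrected before the analysis.

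**What to change.** - **Section 8.2.2:** define PFS as time from enrolment to the first of progression, relapse or death from any cause, and censor patients who are alive without progression.
- **Section 8.1 and the synopsis:** count patients who are alive and progression-free at one year.
- **Section 8.2:** define TTP separately, with a stated rule for deaths without progression.
- **Section 8.1:** say whether the 30% and 50% rates refer to an endpoint that includes death.

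The cost is a written amendment under section 11.3, and it comes late: this version is dated December 01, 2015, and recruitment was planned to end in December 2015 (synopsis) or July 2013 (section 3.2). The amendment should state that it was made without regard to outcomes. If stage 1 has already been decided, it should also state how any such death among the first 15 patients was counted. Deaths and their causes are already collected, so no new data are needed.

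The reported one-year PFS may be lower than under a reading that ignores deaths. If the 50% target meant progression only, counting deaths as failures lowers power from 81.5% to 76% when 2% of patients die without progression (p = 0.48), and to 64% when 5% do (p = 0.45).

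### Section 8.2.2 censors PFS on being alive at last follow-up rather than at the last disease assessment, so one-year PFS is biased upward if any patient is followed alive beyond the last scan

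*Combined protocol and SAP*

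**What the plan says.** Section 8.2.2 gives the PFS event in these words: "It is defined as the time from enrolment to progression or relapse of lymphoma". The censoring rule follows: "Patients alive at last follow-up will be censored". Section 8.2.1 uses the identical sentence for overall survival. Section 8.4 adds only that Kaplan-Meier is used where there is censoring, on all enrolled subjects. No section names a censoring date for PFS or refers to the last disease evaluation.

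The two kinds of follow-up run on different schedules:

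- Section 6.1.2: "Patient survival status will be determined every four weeks during the study treatment", and at longer intervals afterwards.
- Section 6.5.3, for the on-treatment period: "Disease status evaluation (contrasted total body CT scan every 4 months".
- Section 6.5.4 lists disease evaluation for one year after stopping drug, with no interval or imaging method. Section 6.5.5 lists it with CT in long-term follow-up.

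The primary test in section 8.1 is a count: "If there are 5 or fewer patients progression-free at one year in these 15 patients, the study will be stopped", and then "The null hypothesis will be rejected if 19 or more patients progression-free at one year are observed in 47 patients". No rule says how a patient without a one-year assessment is classified in that count.

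**The concern.** For overall survival, being alive means that no event has occurred. For PFS it does not, because a living patient may have progressed undetected since the last scan. Take a patient last evaluated at month 8 and known alive at month 14. If last follow-up means last contact, the Kaplan-Meier curve carries this patient as event-free through month 12, although nothing was observed after month 8.

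The protocol offers routes to this situation. Section 4.3.1 lists stopping drug for toxicity as a regular end of study participation, while section 6.5.4 expects disease evaluation after discontinuation; the two need reconciling. Section 4.3.2 allows withdrawal at any time. Individual scans can also be missed.

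The error has one direction. It raises the one-year PFS, which is the primary endpoint, and the trial is single-arm, so no comparator carries the same error.

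**Working it through.** **1. The plan's own figures.** The section 8.1 rule is to stop at 5 or fewer of 15 and to reject at 19 or more of 47, with null 0.30 and alternative 0.50. With X1 ~ Bin(15, p) and X2 ~ Bin(32, p):

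P(reject) = Σ over x = 6 to 15 of P(X1 = x) · P(X2 ≥ 19 − x).

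This gives 0.0588 at p = 0.30 (the plan states 5%) and 0.815 at p = 0.50 (the plan states 80%). The excess of 0.0588 over 5% comes from the boundary and is a separate matter. Here 0.0588 serves only as the baseline.

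**2. Progression missed between scans, per patient.** Assume a constant hazard, so that PFS at month t is p^(t/12). For a patient free at month 8, the chance of progressing by month 12 is 1 − p^(1/3):

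- p = 0.30: 1 − 0.669 = 0.331
- p = 0.50: 1 − 0.794 = 0.206

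**3. Effect on the one-year Kaplan-Meier estimate.** The documents give no share of patients who are alive but no longer scanned, so the share q is assumed, from 0% to 20%. Further assumptions: scans at months 4, 8 and 12; scanning stops at a time uniform over year 1 and unrelated to progression; those patients are followed alive past month 12 with no later progression recorded.

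A patient who stops before month 4 has no scan and always appears free. One who stops in months 4–8 appears free if free at month 4. One who stops in months 8–12 appears free if free at month 8. Among those who stop, the apparent one-year PFS is

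m = (1 + p^(1/3) + p^(2/3)) / 3.

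- p = 0.30: m = (1 + 0.669 + 0.448)/3 = 0.706
- p = 0.50: m = (1 + 0.794 + 0.630)/3 = 0.808

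Nobody is censored before month 12, so the Kaplan-Meier value is the simple mixture (1 − q)·p + q·m:

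| q | truth 0.30 | truth 0.50 |
|---|---|---|
| 0% | 0.300 | 0.500 |
| 5% | 0.320 | 0.515 |
| 10% | 0.341 | 0.531 |
| 20% | 0.381 | 0.562 |

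**4. The same patients censored at the last scan.** Each four-month interval is then estimated only from patients scanned at its end, giving p^(1/3) per interval and p^(1/3) · p^(1/3) · p^(1/3) = p. The estimate returns to 0.30 or 0.50 for every q.

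**5. If such patients also entered the 19/47 count as successes.** Putting the apparent null rates into the formula of step 1 gives P(reject) of about 0.10, 0.16 and 0.32 for q = 5%, 10% and 20%, against 0.0588.

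**6. If they were all counted as failures instead.** The success probability becomes p(1 − q):

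| q | P(reject), truth 0.30 | P(reject), truth 0.50 |
|---|---|---|
| 10% | at 0.27: 0.022 | at 0.45: 0.642 |
| 20% | at 0.24: 0.006 | at 0.40: 0.411 |

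**The case against.** The strongest reply is that section 8.2.2 says who is censored, not on what date. In section 6.5.5, follow-up is a visit that includes disease evaluation with CT, so last follow-up may itself be an assessed visit. Patients on treatment are examined every one to two weeks. Disease evaluation is scheduled after discontinuation. Section 6.1.2 ends survival follow-up at progression, so it is not a stream wholly separate from disease status. A patient who withdraws consent would often be lost to survival follow-up as well, and the two dates would then coincide.

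Much of this stands. It means that the bias may be small or absent, and that its size cannot be read from the documents. It does not supply a rule for the patients in whom the dates differ, and the sentence as written points to vital status for them. It is also too literal to complain that the sentence fails to require freedom from progression: the sentence before it makes progression the event.

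A reader might infer that patients who are alive but unscanned are counted as progression-free in the 19/47 rule, so that the type I error is 16% or 32%. The documents do not support that. Section 8.1 refers to patients observed progression-free, and neither section says how a censored patient enters the count. The figures in step 5 of the working show what would follow from one possible handling.

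**Conclusion.** The point holds in conditional form. The PFS censoring rule is keyed to being alive, and nothing in the plan links it to a disease assessment. For any patient followed alive beyond the last evaluation, that biases the Kaplan-Meier one-year PFS upward, towards rejecting the 30% null. A true 30% reads about 32%, 34% or 38% when 5%, 10% or 20% of patients are no longer scanned in year 1. Those values rest on the assumed share, a constant hazard, uniform stopping times unrelated to progression, and no progression recorded later. They are scenarios, not bounds.

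It would go too far to say that one-year PFS is overstated in this trial. The bias is zero if scans continue as sections 6.5.3 to 6.5.5 schedule them, and the documents give no share of unscanned patients.

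The same definition has a related gap. Death is not listed as a PFS event despite the endpoint's name, and a careless repair of the censoring sentence would make that worse.

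**What to change.** In section 8.2.2, replace the censoring sentence with: *Patients alive and without progression or relapse are censored at the date of the last disease evaluation showing no progression.* State in the same section that death without progression is a PFS event. The word *alive* matters: a sentence censoring everyone without progression would censor those deaths and inflate PFS in the same direction. Keep the current sentence for overall survival only.

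For section 8.1:

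- Do not count a patient as progression-free at one year on vital status alone.
- Prespecify how patients without a one-year assessment are classified, including a window around the one-year scan so that one done a few days early still qualifies.
- Report the Kaplan-Meier one-year estimate, censored at the last assessment, with its confidence interval beside the 19/47 count.

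The change to 8.2.2 is a matter of wording and needs no new data. Its price is a slightly lower or wider PFS estimate. It removes the bias only if stopping scans is unrelated to progression. The classification rule in 8.1 is a real trade-off. Counting all unassessed patients as failures is conservative, but it lowers power from 81.5% to about 64% if 10% are unassessed and 41% if 20% are. The choice should therefore be made and written down before the data are analysed.
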